### 7.1. Discontinuation from Study Treatment

#### 7.1.1. Discontinuation from Study Treatment

The following criteria must be followed for discontinuation from study treatment. Patients will enter into the Post-Treatment Follow-Up Period (Period 4) if they discontinue from study treatment.

- [1] Discontinuation of the investigational product for abnormal liver tests should be considered by the investigator when a patient meets one of the following conditions, after consultation with the Lilly designated medical monitor:
  - ALT or AST >8xULN
  - ALT or AST >5xULN for more than 2 weeks
  - ALT or AST >3xULN and total bilirubin level >2xULN or prothrombin time >1.5xULN
  - ALT or AST >3xULN with the appearance of fatigue, nausea, vomiting, right upper-quadrant pain or tenderness, fever, rash, and/or eosinophilia (>5%)
  - alkaline phosphatase >2.5xULN and total bilirubin >2xULN
  - alkaline phosphatase >2.5xULN with the appearance of fatigue, nausea, vomiting, right upper quadrant pain or tenderness, fever, rash, and/or eosinophilia (>5%)
- [2] Other laboratory tests (**Note:** Laboratory test(s) that may result in discontinuation based on a single result may be repeated only once if there is a technical error or clinical reason to believe a result may need to be retested. Laboratory tests can only be repeated after consultation with Lilly medical. Investigational product should not be administered in these cases until retest result is available.):
  - Neutrophil (segmented) counts (see safety monitoring for neutropenia in Section [8.4.10.1](#)):

- $<500$  cells/ $\mu\text{L}$  ( $<0.50 \times 10^3/\mu\text{L}$  or  $<0.50$  GI/L)
  - $\geq 500$  and  $<1000$  cells/ $\mu\text{L}$  ( $\geq 0.50 \times 10^3/\mu\text{L}$  and  $<1.00 \times 10^3/\mu\text{L}$  or  $\geq 0.50$  GI/L and  $<1.00$  GI/L) (based on 2 test results; the second test performed within 1 week from knowledge of the initial result)
  - $\geq 1000$  and  $<1500$  cells/ $\mu\text{L}$  ( $\geq 1.00 \times 10^3/\mu\text{L}$  and  $<1.50 \times 10^3/\mu\text{L}$  or  $\geq 1.00$  GI/L and  $<1.50$  GI/L) (based on 3 test results as specified in Section 8.4.10.1)
    - AND - a concurrent infection
  - Total WBC count  $<2000$  cells/ $\mu\text{L}$  ( $<2.00 \times 10^3/\mu\text{L}$  or  $<2.00$  GI/L).
  - Lymphocyte count  $<500$  cells/ $\mu\text{L}$  ( $<0.50 \times 10^3/\mu\text{L}$  or  $<0.50$  GI/L).

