  - Platelet count  $<50,000$  cells/ $\mu\text{L}$  ( $<50 \times 10^3/\mu\text{L}$  or  $<50$  GI/L).
- [3] The patient experiences a severe AE, an SAE, or a clinically significant change in a laboratory value that, in the opinion of the investigator, merits the discontinuation of the investigational product and appropriate measures being taken. In this case, Lilly or its designee is to be notified immediately. Refer to Section 8.2.
- [4] Clinically significant systemic hypersensitivity reaction following SC administration of investigational product that does not respond to symptomatic medication or results in clinical sequelae.
- [5] The patient becomes pregnant.
- [6] The patient develops a malignancy.

**Note:** Patients may be allowed to continue if they develop no more than 2 nonmelanoma skin cancers during the study.

- [7] Enrollment in any other clinical trial involving an investigational product or enrollment in any other type of medical research judged not to be scientifically or medically compatible with this study.
- [8] The patient, at any time during the study, scores a 3 for Item 12 (Thoughts of Death or Suicide) on the QIDS-SR16

-OR-

develops active suicidal ideation with some intent to act with or without a specific plan (yes to question 4 or 5 on the “Suicidal Ideation” portion of the Columbia–Suicide Severity Rating Scale [C-SSRS])

-OR-

develops suicide-related behaviors as recorded on the C-SSRS.

It is recommended that the subject be assessed by a psychiatrist or

appropriately trained professional to assist in deciding whether the subject is to be discontinued from the study.

- [9] The patient develops any condition or contraindication as addressed in the local labeling for adalimumab that would preclude the patient from continuing in this protocol.
- [10] The investigator or attending physician decides that the patient is to be withdrawn from study treatment.
- [11] The patient requests to be withdrawn from study treatment.
- [12] Lilly or its designee stops the patient's participation in the study or Lilly stops the study for medical, safety, regulatory, or other reasons consistent with applicable laws, regulations, and good clinical practice (GCP).
- [13] The patient becomes HBV DNA positive, at which time the patient is to be referred to a specialist physician. Discussion of the timing of discontinuation from the study and from study treatment is provided in Section 8.4.10.2.

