#### **8.4.10.2. Hepatitis B Monitoring**

Patients that are HBcAb+ at screening, regardless of other hepatitis B testing results, will have a serum HBV DNA specimen obtained to be analyzed by the central laboratory. Such patients that are determined to be HBV DNA negative (undetectable) may be enrolled into the study with required HBV DNA monitoring every 3 to 4 months during treatment and 12 weeks after the last dose of ixekizumab. Patients that are found to be HBV DNA positive (detectable) at screening will be excluded from the trial.

If the result of any subsequent HBV DNA testing is positive, the patient is to be discontinued from the study treatment, is to continue safety follow up, and is to receive appropriate follow-up medical care, including consideration for antiviral therapy. A specialist physician in the care of patients with hepatitis (for example, infectious disease or hepatologist subspecialists) is to be consulted and potentially start antiviral therapy prior to discontinuation of any immunosuppressant or immunomodulatory therapy (including investigational drug). Timing of discontinuation from the study and of any immunosuppressant/immunomodulatory therapy

(including investigational product) needs to be based on the recommendations of the consulting specialist physician in conjunction with the investigator and medical guidelines/standard of care.

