- n A Self-Harm Follow-Up Form is to be completed for each discrete self-harm event identified on C-SSRS and the Self-Harm Supplement Form
- o HLA-B27 test will be performed centrally
- p Approval from the Lilly clinical research physician or clinical research scientist must be obtained before a CRP retest is permitted. If the CRP lab is retested, the most recent value will be used for randomization.
- q In countries where the QuantiFERON®-TB Gold test or T-SPOT® is available, either test may be used instead of the PPD TB test. The QuantiFERON®-TB Gold test may be performed locally or centrally; the T-SPOT® must be performed locally. PPD tests must be read 2-3 days after Visit 1. Refer to Section 8.4.6 for more details.
- r For female patients  $\geq 40$  and  $< 60$  years of age who have had a cessation of menses for at least 12 months, an FSH test will be performed to confirm non-childbearing potential (FSH  $\geq 40$  mIU/mL or  $\geq 40$  IU/L). FSH test will be performed centrally.
- s All patients will be tested for HBV at screening. Patients that are HBcAb+ at screening, regardless of HBsAb status, will have a serum HBV DNA obtained by the central laboratory. Patients that are found to be HBV DNA positive (detectable) at screening will be excluded from the trial. Patients that are HBV DNA negative (undetectable) may be enrolled into the study with required HBV DNA monitoring every 3 months during treatment and 12 weeks after the last dose of ixekizumab. If the result of the HBV DNA testing is positive, the patient is to be discontinued from the study and is to receive appropriate follow-up medical care (refer to Section 8.4.10.2 for further information regarding the timing of discontinuation).

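### A positive HBV DNA result means leaving the study in one place and stopping treatment with follow-up in another, and one timetable row puts the last hepatitis B test short of the protocol's own 12 weeks

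*Protocol*

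**What the plan says.** **Disposition.** Footnote s in Protocol Appendix 2 states: "If the result of the HBV DNA testing is positive, the patient is to be discontinued from the study". It adds that the patient is to receive suitable medical care and ends with a pointer: "refer to Section 8.4.10.2 for further information regarding the timing of discontinuation". Section 8.4.10.2 says of the same event that "the patient is to be discontinued from the study treatment, is to continue safety follow up".

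Criterion [13] lists HBV DNA positivity under Section 7.1.1, which covers discontinuation from study treatment. The general rule there is: "Patients will enter into the Post-Treatment Follow-Up Period (Period 4) if they discontinue from study treatment". The criterion itself mentions both kinds of discontinuation: "Discussion of the timing of discontinuation from the study and from study treatment is provided in Section 8.4.10.2".

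**Monitoring.** Footnote s asks for "required HBV DNA monitoring every 3 months during treatment and 12 weeks after the last dose of ixekizumab". Section 8.4.10.2 asks for "required HBV DNA monitoring every 3 to 4 months during treatment and 12 weeks after the last dose of ixekizumab".

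**Follow-up timing.** Footnote aa in Appendix 2 gives Visits 801 and 802 to every patient on investigational product who discontinues early, at 4 and 12 weeks after the last visit. The Period 4 timetable for patients who stop before Week 16 instead fixes Visit 802 by study week. For a patient who stops at Week 8 it gives Visit 801 at Week 12 and Visit 802 at Week 16. In that table HBV testing is marked at Visits 801 and 802 but not at Visit 803, and each visit has a window of ±14 days.

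**The concern.** In this protocol, leaving the study and stopping treatment are separate events. Section 7 collects a reason and a date for each. Section 7.1.1 sends treatment discontinuers to Period 4, and Section 7.1.3 deals with permanent discontinuation from the study. Footnote s and Section 8.4.10.2 therefore assign the same laboratory result to two different outcomes. The cross-reference does not settle which applies, because it covers timing only.

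The group affected is the one for which the protocol prescribes extra monitoring: patients enrolled as HBcAb positive and HBV DNA negative. The disposition also matters for the data. The Follow-Up Population requires entry into Period 4, and the SAP's protocol deviation table (Table RHBV.6.12) lists becoming HBV DNA positive under violation of discontinuation criteria, so a reader needs to know what compliance means.

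The timetable raises a second question. Both hepatitis B texts require a test 12 weeks after ixekizumab is last given, and one row of the early-discontinuation timetable may not deliver it.

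**Working it through.** There is no statistical figure to reproduce. The check is a comparison of passages plus arithmetic on scheduled weeks.

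**1. Disposition, side by side**

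| Place | What is discontinued | What follows |
|---|---|---|
| Appendix 2, footnote s | the study | medical care; Section 8.4.10.2 cited for timing |
| Section 8.4.10.2 | study treatment | safety follow-up continues |
| Section 7.1.1, criterion [13] | study treatment (by its place in the list) | Period 4; Section 8.4.10.2 cited for timing of both kinds of discontinuation |

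Section 8.4.10.2 also goes on to speak of the timing of discontinuation from the study, to be guided by the consulting specialist. No single passage states one unambiguous outcome.

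**2. Visit 802 in the pre-Week-16 timetable**

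Gap from last visit = Visit 802 week − discontinuation week.

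| Stops at | Visit 802 | Gap (weeks) |
|---|---|---|
| Week 1 | Week 16 | 16 − 1 = 15 |
| Week 2 | Week 16 | 16 − 2 = 14 |
| Week 4 | Week 16 | 16 − 4 = 12 |
| Week 8 | Week 16 | 16 − 8 = 8 |
| Week 12 | Week 24 | 24 − 12 = 12 |

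Only the Week 8 row falls short of the 12 weeks in footnote aa. The Week 1 and Week 2 rows run longer.

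**3. The same Week 8 row, measured from the last ixekizumab dose**

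The two hepatitis B texts count from the last dose, not the last visit. Under Table RHBV.2, Q2W doses fall at Weeks 0, 2, 4, 6, 8 and so on, and Q4W doses at Weeks 0, 4, 8 and so on. The last dose depends on whether the Week 8 dose was taken. The ±14-day window moves Visit 802 between Weeks 14 and 18.

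| Last ixekizumab dose | Nominal gap (weeks) | Range with window (weeks) |
|---|---|---|
| Week 8 (either regimen, dose taken) | 16 − 8 = 8 | 6 to 10 |
| Week 6 (Q2W, Week 8 dose not taken) | 16 − 6 = 10 | 8 to 12 |
| Week 4 (Q4W, Week 8 dose not taken) | 16 − 4 = 12 | 10 to 14 |

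If the Week 8 dose was taken, the visit cannot reach 12 weeks even at the late edge of the window. If the last dose was at Week 6, it reaches 12 only at that edge.

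**4. Monitoring interval on treatment**

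The Schedule of Activities places HBV tests at Weeks 0, 12, 24, 36, 44 and 52. The gaps are 12, 12, 12, 8 and 8 weeks. The longest, 12 weeks, is compatible with a 3-month interval and does not exceed what the 3-to-4-month wording allows.

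**The case against.** The strongest reply is that the footnote is loose shorthand. Criterion [13] and the Period 4 rule in Section 7.1.1 point to stopping treatment and entering follow-up. Footnote aa, in the same appendix, gives safety visits to dosed patients who discontinue at any time. Section 7.1.3 requires end-of-study procedures for those who leave early, and footnote s itself asks for follow-up care. Section 8.4.10.2 can be read as a sequence: treatment stops, safety follow-up continues, and study exit is timed with the specialist.

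Much of this stands. A reader might infer that a site working from the schedule would end all follow-up of a patient with viral reactivation. The documents do not support that, because footnote aa alone makes it unlikely. What remains is that footnote s names a different disposition from Section 8.4.10.2 and does not defer to it on that question.

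On the timetable, a reader might infer that every Week 8 discontinuer is tested four weeks early. That is also too strong. The 8 weeks is counted from the last visit, whereas the requirement counts from the last dose, so the nominal shortfall is 4, 2 or 0 weeks depending on that dose. One row of five is affected, and HBV is also tested at the early termination visit and at Visit 801. But those tests come earlier still, so they do not supply the 12-week test.

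Finally, the interval wording might be read as two testing schedules. It is not, because the visit grid fixes the tests and satisfies both texts.

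**Conclusion.** Two inconsistencies hold.

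- **Disposition.** Footnote s has a newly HBV DNA positive patient leave the study; Section 8.4.10.2 and criterion [13] have the patient leave treatment and stay in safety follow-up. Complete loss of follow-up is unlikely, but the instructions conflict.
- **Last HBV test.** For a Week 8 discontinuer, the last scheduled test is 8 weeks after the last visit against 12 in footnote aa. It is nominally 8, 10 or 12 weeks after the last ixekizumab dose against the 12 required.

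The different monitoring intervals are a minor wording mismatch with no operational effect.

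The dose-based figures assume dosing on the nominal schedule up to the last dose. The number of HBcAb-positive, HBV DNA-negative enrollees is not given, so the number of patients at issue cannot be stated. The Week 16 primary analysis does not depend on any of this, since stopping treatment before Week 16 counts as nonresponse under NRI either way. The matter is one of patient safety instructions and follow-up data. It should be corrected, but it does not threaten the efficacy conclusions.

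**What to change.** Reconcile footnote s, footnote aa and the pre-Week-16 timetable in Appendix 2 with Section 8.4.10.2 and criterion [13] in Section 7.1.1. They should state:

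- one disposition for a positive HBV DNA result;
- a Period 4 schedule in which the Week 8 row, footnote aa and the required post-treatment HBV test agree;
- one wording for the on-treatment monitoring interval.

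Which disposition and which test time apply is for the sponsor's medical team. In revising the Week 8 row, note that SAP Section 6.10.5.3 relies on a follow-up visit at Week 16 for efficacy data after treatment discontinuation, so that purpose and the HBV test need to be considered together.

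The cost is wording in a protocol amendment or a clarification letter to sites. No analysis, sample size or endpoint changes.

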**Treatment Groups and Duration:**

Study RHBV has 4 treatment groups during the 16-week Blinded Treatment Dosing Period; ixekizumab 80 mg Q4W, ixekizumab 80 mg Q2W, placebo, and adalimumab 40 mg Q2W at 1:1:1:1 ratio. Randomization will be stratified by country and baseline high sensitivity C-reactive protein (CRP) status (nonelevated or elevated, elevated defined as  $>5.00$  mg/L). All patients randomized to an ixekizumab treatment group will receive a starting dose of ixekizumab 80 mg or 160 mg (1:1 ratio) at Week 0 followed by ixekizumab 80 mg Q4W or Q2W thereafter; all patients randomized to adalimumab will receive adalimumab 40 mg Q2W from Week 0 to Week 14. All administrations are SC. At Week 16, placebo patients will be rerandomized at a 1:1 ratio to ixekizumab 80 mg Q2W or Q4W with a 160 mg starting dose. At Week 16, adalimumab patients will be re-randomized to ixekizumab 80 mg Q4W or Q2W. All patients will be on an ixekizumab regimen for the Extended Treatment Period (Weeks 16 to 52) (for safety reasons, adalimumab patients will have a 6-week washout period before receiving ixekizumab). As needed, investigators can modify concomitant medication during the wash-out period to maintain symptom control. The study duration will be up to 1 year for ixekizumab administration, and up to 1 year and approximately 4 months for study participation over 4 periods ([1] Screening Period: up to 42 days; [2] Blinded Treatment Dosing Period: 16 weeks; [3] Extended Treatment Period: 36 weeks; [4] Post-Treatment Follow-Up Period: at least 12 weeks after the date of the patient's early termination visit [ETV] or last regularly scheduled visit). Patients who complete Study RHBV may have the opportunity to continue into a long term study instead of the Post-Treatment Follow-Up Period.

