### **8.2.1. Serious Adverse Events**

An SAE is any AE from this study that results in one of the following outcomes:

- death
- initial or prolonged inpatient hospitalization
- a life-threatening experience (that is, immediate risk of dying)
- persistent or significant disability/incapacity
- congenital anomaly/birth defect

- important medical events that may not be immediately life-threatening or result in death or hospitalization but may jeopardize the patient or may require intervention to prevent one of the other outcomes listed in the definition above.

If an SAE occurs after signing the ICF, but prior to receiving investigational product, it needs to be reported ONLY if it is considered reasonably possibly related to study procedure.

Study site personnel must alert Lilly or its designee of any SAE within 24 hours of investigator awareness of the event via a sponsor-approved method. If alerts are issued via telephone, they are to be immediately followed with official notification on study-specific SAE forms. This 24-hour notification requirement refers to the initial SAE information and all follow-up SAE information.

Pregnancy (during maternal or paternal exposure to investigational product) does not meet the definition of an AE. However, to fulfill regulatory requirements any pregnancy (during maternal or paternal exposure to investigational product) must be reported following the SAE process and data are to be collected on the outcome for both mother and fetus.

Investigators are not obligated to actively seek AEs or SAEs in subjects once they have discontinued and/or completed the study (the patient summary CRF has been completed). However, if the investigator learns of any SAE, including a death, at any time after a subject has been discharged from the study, and he/she considers the event reasonably possibly related to the study treatment or study participation, the investigator must promptly notify Lilly.

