**Schedule of Activities, Protocol I1F-MC-RHBV (Period 4)**

Patients who discontinue treatment **prior** to Week 16 are to use the time table below to schedule activities for Post-Treatment Follow-Up visits.

Discontinued Week No. (Visit No.)	Corresponding V801 (LV + 4 weeks)	Corresponding V802	Corresponding V803 (LV + 24 weeks)
Week 1 (Visit 3)	Week 5	Week 16	Week 25
Week 2 (Visit 4)	Week 6	Week 16	Week 26
Week 4 (Visit 5)	Week 8	Week 16	Week 28
Week 8 (Visit 6)	Week 12	Week 16	Week 32
Week 12 (Visit 7)	Week 16	Week 24	Week 36

	Post-Treatment Follow-Up for Patients Discontinuing Treatment prior to Week 16 (Period 4)aa		
	Required Follow-Up Visits		As-Needed Follow-Up Visits
CRF (V) Visit Number	V801	V802	V803 and onwards
Study Days	±14d	±14d	±14d
Concomitant medications	X	X	X
Vital signs (BP and pulse) d	X	X	X
Weight bb	X	X	X
Preexisting conditions and medical history h	X	X	X
Adverse events	X	X	X
C-SSRS a	X	X	X
Self-Harm Supplement Form n	X	X	X
HBV	X s	X s	
Serum chemistry	X	X	X
Hematology	X	X	X
Nonpharmacogenetic biomarker exploratory storage samples (urine, serum, plasma, RNA, and whole blood) v	X w	X w	
Immunogenicity testing x	X	X	
PK sampling x,y	X	X	
Patient Global Assessment of Disease Activity NRS	X	X	
Spinal pain	X	X	
BASFI	X	X	
BASDAI	X	X	
CRP	X	X	

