- t Only for females of childbearing potential. Serum pregnancy test will be done at Visit 1 only, and will be performed centrally. Patients determined to be pregnant will be discontinued from treatment and will no longer be administered investigational product (see Section 7.1). Patients will undergo urine pregnancy testing at the clinic during scheduled visits through Week 52. Additional urine pregnancy testing can be performed at the investigator's discretion. If required per local regulations, testing can occur at other intervals during the study treatment period and/or follow up period. Patients determined to be pregnant will be discontinued from treatment and will no longer be administered investigational product (see Section 7.1).
- u For the fasting lipid profile patients are not to eat or drink anything except water for 12 hours prior to test.
- v Where collection is allowed by local regulations.
- w Only serum and plasma are collected at this visit.
- x Immunogenicity samples may also be analyzed for ixekizumab serum concentration to facilitate in the interpretation of immunogenicity data. An additional blood sample will be collected, when possible, for any patient who experiences a potential systemic allergic/hypersensitivity reaction during the study as judged by the investigator.
- y PK samples are to be collected before investigational product injection.
- z The Week 52 MRI may be collected up to 10 days **prior** to Week 52 (Visit 15).

- aa Patients receiving investigational product who discontinue at any time prior to the end of the study or who complete the study (Week 52) and do not choose to enroll in Study RHBV, will have safety Follow-Up Visits 801 and 802 at 4 and 12 weeks (respectively) after the date of their last visit. Visit 803 will occur if a patient's neutrophil counts have not returned to the criteria defined in Section [8.4.10.1](#).
- bb Weight is only captured on eCRF at V2, V8, V10, V15, and/or ETV. Body weight collected at other visits is used only for calculation of creatinine clearance.
- cc If not completed at Visit 2, the sample should be collected as soon as possible at the next scheduled visit.

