6.10.5.3. Analysis Including Efficacy Data Post Treatment Discontinuation

Per recommendation in the 2010 National Research Council report *The Prevention and Treatment of Missing Data in Clinical Trials*, additional efficacy data for patients who prematurely discontinued Period 2 are collected during the Post-Treatment Follow-Up Period

(Period 4). Patients who discontinue treatment prior to Week 16 are instructed to schedule the Post-Treatment Follow-Up visit such that the post-treatment data will be collected 16-week after initial randomization. The efficacy data of ASAS40 at Week 16 will be summarized by treatment group, but no formal statistical comparison will be performed.

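### For patients who stop treatment at Week 8, the timetable puts the last required follow-up visit 8 weeks after the last visit, against the protocol's own 12-week minimum

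*Protocol*

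**What the plan says.** Protocol Appendix 2, footnote aa, applies to patients on investigational product who discontinue at any time before the end of the study, and to completers who do not enter the extension. They "will have safety Follow-Up Visits 801 and 802 at 4 and 12 weeks (respectively) after the date of their last visit". V803 is added only when neutrophils have not recovered. The Protocol Synopsis (Treatment Groups and Duration) describes the same period as "Post-Treatment Follow-Up Period: at least 12 weeks after the date of the patient's early termination visit" or last regularly scheduled visit. The notes to Figure RHBV.1 confirm that V801 and V802 are required for all patients and that V803 depends on neutrophil counts.

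For patients who stop before Week 16, the Period 4 schedule in Appendix 2 has its own timetable, and sites are "to use the time table below to schedule activities for Post-Treatment Follow-Up visits". The Week 8 row reads "Week 8 (Visit 6) Week 12 Week 16 Week 32": discontinuation week, then V801, V802 and V803. Footnote aa is attached to the heading of the assessment table for these same patients.

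SAP Section 6.10.5.3 explains the Week 16 placement. Early discontinuers are "instructed to schedule the Post-Treatment Follow-Up visit such that the post-treatment data will be collected 16-week after initial randomization", so that ASAS40 at Week 16 can be summarised descriptively.

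V802 in this table also holds the last scheduled hepatitis B test. Protocol Section 8.4.10.2 calls for "required HBV DNA monitoring every 3 to 4 months during treatment and 12 weeks after the last dose of ixekizumab" in patients who are core-antibody positive and HBV DNA negative. Footnote s repeats the 12-week requirement.

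**The concern.** Two current instructions attached to the same patients cannot both be followed. A site that uses the timetable for a Week 8 stop ends required safety follow-up before the 12 weeks set by footnote aa and the synopsis. A site that follows footnote aa has to depart from the timetable.

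At stake are the required adverse event, C-SSRS, chemistry, haematology and immunogenicity assessments, which would end 4 weeks early. After that, Protocol Section 8.2.1 applies: "Investigators are not obligated to actively seek AEs or SAEs in subjects once they have discontinued and/or completed the study". For the hepatitis B subgroup, the last scheduled DNA test may also come before the required 12 weeks after the last ixekizumab dose.

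**Working it through.** **Confirming the last visit (LV).** The timetable labels V801 as LV + 4 weeks and V803 as LV + 24 weeks. For the Week 8 row, 12 − 4 = 8 and 32 − 24 = 8, so LV is Week 8. Both labels reproduce in all five rows.

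**Interval from LV to V802** = V802 week − discontinuation week. The window is ±14 days, or ±2 weeks.

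| Stop | V801 | V802 | V803 | V802 − LV (weeks) | With window (weeks) | Nominally at least 12? |
|---|---|---|---|---|---|---|
| Week 1 | 5 | 16 | 25 | 15 | 13 to 17 | yes |
| Week 2 | 6 | 16 | 26 | 14 | 12 to 16 | yes |
| Week 4 | 8 | 16 | 28 | 12 | 10 to 14 | yes |
| Week 8 | 12 | 16 | 32 | 8 | 6 to 10 | **no, 4 short** |
| Week 12 | 16 | 24 | 36 | 12 | 10 to 14 | yes |

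The plan's 12 weeks is met nominally in four rows and missed in one. The Week 1 and Week 2 rows exceed the fixed 12 weeks of footnote aa but satisfy the synopsis minimum. In the Week 8 row even the latest permitted date is 12 − 10 = 2 weeks short.

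**Consistency with other text.** Protocol Section 8.4.10.1.2 places V802 8 weeks after V801 unless otherwise specified, and V803 12 weeks after V802. The Week 8 row gives 16 − 12 = 4 and 32 − 16 = 16. SAP Section 6.12.4.2 also ties V802 to 12 weeks after entry to follow-up.

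**Hepatitis B test.** Interval = V802 week − week of last ixekizumab dose. Table RHBV.2 gives active doses at Weeks 0, 2, 4, 6 and 8 for Q2W and at Weeks 0, 4 and 8 for Q4W.

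| Last dose | V802 at Week 16 | Shortfall against 12 weeks | V802 at Week 20 |
|---|---|---|---|
| Week 4 (Q4W) | 16 − 4 = 12 | none | 20 − 4 = 16 |
| Week 6 (Q2W) | 16 − 6 = 10 | 2 weeks | 20 − 6 = 14 |
| Week 8 (if dosed at that visit) | 16 − 8 = 8 | 4 weeks | 20 − 8 = 12 |

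These are nominal dates. At the latest permitted V802 (Week 18), a last dose at Week 6 gives 18 − 6 = 12 weeks, which just meets the rule. A last dose at Week 8 gives 18 − 8 = 10, which does not. The rule does not apply to placebo and adalimumab patients (2 × 80 = 160 of the planned 320), who have had no ixekizumab by then.

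**The case against.** The strongest defence is that the timetable is a specific, purposeful exception to a general rule. The V802 column, unlike its neighbours, carries no LV label, and SAP Section 6.10.5.3 gives the reason for Week 16. The deliberate purpose stands. It is an efficacy purpose, however, and no text lets it shorten safety follow-up. Footnote aa is on the same table and covers discontinuation at any time. The Week 12 row shows that both aims can be met: efficacy at Week 16 through V801, and V802 at Week 24, which is LV + 12.

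A second argument is that 12 weeks is not a hard floor, because the window already permits 10 weeks in the nominal 12-week rows. That is true, but those rows are centred on 12. The Week 8 row only reaches 10 at its latest permitted date.

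Third, the hepatitis B duty is tied to the dose, so an early V802 does not cancel it. Protocol Section 7 withholds product on permanent discontinuation, which makes dosing at the Week 8 visit less likely. Both points stand and narrow the issue mainly to Q2W patients last dosed at Week 6. The schedule still provides no test after V802 for them, and its nominal date is early.

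Finally, other safeguards remain. The schedule is a minimum frequency (Protocol Section 4.1). Adverse events that led to discontinuation are followed until they resolve, stabilise or are explained (Section 8.2). Neutrophil recovery is tracked (Section 8.4.10.1.3), and related serious events learned of later must be reported (Section 8.2.1). These limit the loss but do not remove the contradiction.

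**Conclusion.** The concern holds. For a Week 8 stop, the last required follow-up visit is nominally 8 weeks after the last visit (6 to 10 with the window), 4 weeks below the 12 weeks stated in footnote aa and the synopsis. It is the only row that fails nominally.

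The consequence is limited. Adverse events that caused discontinuation and unrecovered neutrophils are still followed, and Period 4 safety is only summarised descriptively (SAP Section 6.1.4). The primary analysis, power and type I error are untouched: under nonresponder imputation these patients count as nonresponders at Week 16 whenever V802 occurs.

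The hepatitis B shortfall of 2 or 4 weeks is nominal. It depends on the date of the last dose and applies only to core-antibody-positive, DNA-negative patients on ixekizumab. The documents do not say how many patients are expected to stop at Week 8; the number is probably small. The point should be fixed because it concerns a stated safety minimum and is cheap to correct.

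**What to change.** For patients who stop at Week 8:

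- Keep the Week 16 efficacy collection (Patient Global, spinal pain, BASFI, BASDAI, CRP) as an assessment of its own, separate from V802.
- Set V802 at Week 20 (LV + 12 weeks), and make it the end of required safety follow-up and the visit for the final HBV DNA test.

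The DNA test then falls nominally 16, 14 or 12 weeks after a last dose at Week 4, 6 or 8. Because the ±14-day window still applies, the protocol could add that this test is not to be drawn earlier than 12 weeks after the last ixekizumab dose.

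The cost is one amended row, a footnote or column to define the added Week 16 assessment (the table now collects efficacy only at V801 and V802), and one extra visit for each Week 8 discontinuer. The descriptive Week 16 summary in SAP Section 6.10.5.3 keeps its data.
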